The Gross Motor Function Measure (GMFM-66), a standardized clinical tool consisting of 66 items, created to detect gross motor function change in children with CP, is considered a valid outcome measure, sensitive enough to document clinically meaningful improvement, including responsiveness (11, 12) and is the gold standard measure of functional ability in the area of CP (13). The GMFM-66 score reflects the overall level of gross motor capacity (14). Using the Gross Motor Ability Estimator Scoring Software (15), a GMFM-66 score can be obtained using a minimum of 13 items. Due to the included children's high gross motor function (GMFCS level I-II) combined with the need to limit the amount of testing time for the children, a selection of minimum 13 relevant items of the GMFM-66 were chosen for this study.

A potential association between the parents' perception of the family-centeredness of the services they and their children received during the study period (by means of the MPOC 52-weeks follow-up score) and the child's gross motor improvement (change in GMFM-66 score), could indicate that improvement in gross motor function of a child with CP is related to the parents' involvement in the process of care. Thus, an association could serve as an indicator for the health personnel in terms of detecting those families who would benefit from enhanced information, service and care, to improve the child's gross motor function.

List of abbreviations and definition of terms

BMI SDS	Body Mass Index Standard Deviation Score
CP	Cerebral Palsy
FCS	Family-centered services
GDI	Gait Deviation Index
GMFCS	Gross Motor Function Classification System
GMFM-66	Gross Motor Function Measure - 66
MPOC-20	Measure of Processes of Care – 20
IGA	Instrumented Gait Analysis
IQR	Interquartile range
SAP	Statistical Analysis Plan
SD	Standard Deviation

Study aim, hypothesis and outcome measures

Aim

The aim of this secondary analysis (on tertiary outcome measures) of a randomized controlled study is to investigate whether individually tailored interdisciplinary intervention, based on the use of IGA, has a superior effect on perceived experience of FCS compared to 'care as usual' without the use of IGA. The study will furthermore investigate whether the availability of the IGA has a superior effect on gross motor function improvement as well as investigate potential associations between perceived experience of FCS and gross motor function improvement.

Primary hypothesis and outcome

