The primary hypothesis to be tested is that the use of IGA in the planning of individually tailored interdisciplinary intervention will result in a higher parentally perceived experience of FCS evaluated by the MPOC-20, compared to 'care as usual' in relatively young children with CP at GMFCS level I-II.

The primary analysis is between-group change difference in all five MPOC-20 domains at 52-weeks. The five MPOC-20 domains comprise *enabling and partnership, providing general information, providing specific information about the child, respectful and supportive service and coordinated and comprehensive care*.

Data for the primary analysis, between-group change difference in MPOC-20₀₋₅₂, will be presented in table 2.

Secondary hypotheses and outcome

a) The above listed hypothesis will be analysed at 26-weeks follow-up.

Outcome measure, between-group change difference in MPOC-20 domains at 26-weeks post start of intervention, will be presented in table 2.

b) The planning of individually tailored interdisciplinary intervention will result in better gross motor function, evaluated by GMFM-66, compared to 'care as usual' in relatively young children with CP at GMFCS level I-II.

Outcome measure, between-group change score in GMFM-66 at 52-weeks post start of intervention, will be presented in table 2.

c) The experience of FCS is associated with gross motor function improvement in a unidirectional or bidirectional relation.

Outcome will be presented as multiple regression analysis in table 3.

Statistical analyses

Data

Descriptive outcome

At inclusion the following descriptive outcomes were collected:

- Sex (female or male)
- Age (in years)
- Weight and height
(used to calculate Body Mass Index Standard Deviation Score (BMI SDS)) (16)
- Cerebral palsy spastic subtype (uni- or bilateral)
- Gross Motor Function Classification System (GMFCS level I or II)
- Randomization group: Intervention (the use of IGA) or control ('care as usual').

The descriptive outcomes will be presented in Table 1.

Outcome measures

- MPOC-20: Parent reported data obtained from a questionnaire with the five domains *enabling and partnership, providing general information, providing specific information about the child, respectful and supportive service, coordinated and comprehensive care*. Data comprise the timepoints at baseline, 26 weeks and 52 weeks post start of intervention and the differences between these timepoints: Δ MPOC-20₀₋₂₆ and Δ MPOC-20₀₋₅₂.

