- GMFM-66: Standardized clinical tool created to detect gross motor function change in children with CP. Data comprise the timepoints at baseline and 52 weeks post start of intervention and the difference between these timepoints: Δ GMFM₀₋₅₂.

Data analyses

Analyses will be performed according to intention-to-treat, with last value carried forward for missing observations.

Descriptive statistics will be summarized as appropriate. Distribution of data will be investigated using normal probability plots and Shapiro–Wilk test, and will be presented with mean and standard deviation (SD) for parametric data and median and interquartile range (IQR) for non-parametric data. Data outliers will be identified with the use of scatterplots.

Between-group change differences will be estimated with a linear model (table 2, model A) in which relevant baseline scores are entered as covariates (table 2, model B). Model specifications will depend on evaluation of distributional properties of collected data and appropriate adaptation of point estimate and variation indicators.

Associations will be evaluated using multiple linear regression. To evaluate whether the child's change in gross motor function is associated to the parent's perceived experience of FCS, MPOC-20 52-weeks follow-up domain scores will be used as the dependent variable and Δ GMFM-66₀₋₅₂ score as the independent variable, adjusted for baseline GMFM-66 score (table 3, model A). Further, potential confounding variables as sex, age, BMI SDS, CP spastic subtype and GMFCS level will be adjusted for as covariates (table 3, model B).

To evaluate whether the parents perceived experience of FCS is associated with the child's change in gross motor function, Δ GMFM-66₀₋₅₂ score will be used as the dependent variable and MPOC-20 52-weeks follow-up domain scores as the independent variable, adjusted for baseline MPOC-20 domain scores (table 3, model A). Further, potential confounding variables as sex, age, BMI SDS, CP type and GMFCS level will be adjusted for as covariates (table 3, model B).

Results will be presented with an alpha of 0.05 and a 95% confidence interval, statistical significance level set at $p<0.05$.

Statistical analysis will be conducted from April 2018 and performed using Stata/IC version 14.2 or later.

Data interpretation

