To investigate whether individually tailored interdisciplinary intervention based on IGA has a superior effect on perceived experience of FCS compared to ‘care as usual’, between-group change score for each of the five MPOC-20 domains will be reported in the primary analysis.

To minimize bias, interpretation of variation of outcome will be defined *a priori*:

- a) If more domains exhibit significantly positive outcomes in one group compared to the other, this group will be considered as superior.
- b) If both groups have the same number of significantly positive domains, neither group will be considered superior.
- c) If neither group has a significant positive domain, neither group will be considered superior.

Tables and figures

Table 1: Demographics and baseline data of included children

	Intervention (n=)	Control (n=)
Sex (girls/boys)		
CP spastic subtype (uni-/bilateral)		
GMFCS level (I-II)		
Age (years)		
Height (m)		
Weight (kg)		
Body Mass Index SDS		
Measure of Processes of Care – 20 domains		
enabling and partnership		
providing general information		
providing specific information about the child		
respectful and supportive service		
coordinated and comprehensive care		
Gross Motor Function Measure - 66		

Reported as mean and standard deviation (SD) or median and interquartile range (IQR).

Table 2: Between-group change difference at 26-weeks and 52-weeks follow up

	Between-group change difference											
	Model A						Model B					
	Baseline to 26 weeks			Baseline to 52 weeks			Baseline to 26 weeks			Baseline to 52 weeks		
	β (95% CI)	R ²	p	β (95% CI)	R ²	p	β (95% CI)	R ²	p	β (95% CI)	R ²	p
Δ MPOC-20 domains												
Δ enabling and partnership												
Δ providing general information												
Δ providing specific information about the child												
Δ respectful and supportive service												
Δ coordinated and comprehensive care												
Δ GMFM-66												

Dependent variable: ΔGMFM-66 or ΔMPOC-20 domains.

Independent variable: Randomization group.

Model A: Unadjusted model.

Model B: Model A adjusted for relevant baseline score.

Abbreviations: GMFM – Gross Motor Function Measure. MPOC – Measure of Processes of Care.

Table 3: Associations between MPOC-20 and GMFM-66

Dependent variable:	Independent variable: ΔGMFM_{0-52} score	Model A			Model B		
		β (95% CI)	R ²	p	β (95% CI)	R ²	p
MPOC-20 52-weeks follow-up domain scores							
enabling and partnership							

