providing general information							
providing specific information about the child							
respectful and supportive service							
coordinated and comprehensive care							

Dependent variable: MPOC domains at 52-weeks follow-up.

Independent variable: ΔGMFM_{0-52} score.

Model A: Adjusted for baseline GMFM.

Model B: Model A adjusted for sex, age, BMI SDS, CP type and GMFCS level.

Abbreviations: GMFM – Gross Motor Function Measure. MPOC – Measure of Processes of Care.

Dependent variable:	Independent variable: MPOC-20 52-weeks follow-up domain scores	Model A			Model B		
		β (95% CI)	R ²	p	β (95% CI)	R ²	p
ΔGMFM_{0-52} score							
enabling and partnership							
providing general information							
providing specific information about the child							
respectful and supportive service							
coordinated and comprehensive care							

Dependent variable: ΔGMFM_{0-52} score

Independent variable: MPOC domains at 52-weeks follow-up

Model A: Adjusted for baseline MPOC-20 domain scores

Model B: Model A adjusted for sex, age, BMI SDS, CP type and GMFCS level.

Abbreviations: GMFM – Gross Motor Function Measure. MPOC – Measure of Processes of Care.

Literature

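### The Table 3 association models omit randomised group, although the plan expects the intervention to raise both MPOC-20 and GMFM-66

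*SAP*

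**What the plan says.** The SAP's Data analyses section sets out two sets of multiple linear regressions for secondary hypothesis c), reported in Table 3.

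- **Direction 1:** each 52-week MPOC-20 domain score on the 0–52-week change in GMFM-66. The footnote reads "Model A: Adjusted for baseline GMFM". For Model B, "potential confounding variables as sex, age, BMI SDS, CP spastic subtype and GMFCS level will be adjusted for as covariates".
- **Direction 2:** the GMFM-66 change on each 52-week MPOC-20 domain score. The footnote reads "Model A: Adjusted for baseline MPOC-20 domain scores". For Model B, "potential confounding variables as sex, age, BMI SDS, CP type and GMFCS level will be adjusted for as covariates".

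Both Table 3 footnotes close the covariate list: "Model B: Model A adjusted for sex, age, BMI SDS, CP type and GMFCS level". The arm enters a model only in Table 2, whose footnote states "Independent variable: Randomization group". Table 3 has no rows or columns by arm, and no stratified or interaction analysis is planned. The SAP does not use the word, but the arms are pooled.

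The primary hypothesis is that use of gait analysis gives higher MPOC-20 scores than usual care. Secondary hypothesis b) is that "The planning of individually tailored interdisciplinary intervention will result in better gross motor function, evaluated by GMFM-66", again compared with usual care. It does not name gait analysis, but the Aim section makes clear that this is the effect meant. The Study synopsis says how a finding under c) would be used: "an association could serve as an indicator for the health personnel in terms of detecting those families who would benefit from enhanced information".

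**The concern.** Under the plan's own hypotheses, randomised group drives both variables in Table 3. Model B is presented as confounder adjustment and takes in five patient characteristics, but it leaves out the one factor that the plan predicts will move both. Randomised group is listed under Descriptive outcome beside those same characteristics, so it is available.

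Adjusting for a baseline score does not help, because a group effect arises after baseline. The five Model B characteristics do not help either. They were recorded at inclusion, are balanced between arms in expectation, and so cannot stand in for the arm.

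What is at stake is the reading of hypothesis c). Suppose the intervention improves parents' experience and motor function by separate routes. Table 3 would then show an association, and the synopsis would have it read as motor improvement being tied to parents' involvement in care and used to pick out families for extra support. If the two group effects had opposite signs, the same omission could hide a real within-arm association.

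**Working it through.** The SAP states no sample size, effect size, SD or correlation for this analysis, so there is no planned figure to reproduce. The check is an illustration under stated assumptions.

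**Inputs**

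- From the SAP: the Model A covariates in each direction, no group term, and a 0.05 significance level.
- Assumed: 1:1 allocation; no relation between MPOC-20 and GMFM-66 within an arm; group effects d1 (MPOC-20) and d2 (GMFM-66 change) in within-arm SD units; total N of 40, 60 or 100; baseline-to-52-week MPOC-20 correlation of 0.5; correlation of −0.3 between baseline GMFM-66 and its change.

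**Step 1: correlation induced by arm alone**

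With 1:1 arms, the arm term contributes d1·d2/4 to the covariance, and d1²/4 and d2²/4 to the variances:

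r = (d1·d2/4) / √[(1 + d1²/4)(1 + d2²/4)]

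- d1 = d2 = 0.3: 0.0225/1.0225 = 0.02
- d1 = d2 = 0.5: 0.0625/1.0625 = 0.06
- d1 = d2 = 0.8: 0.16/1.16 = 0.14
- d1 = d2 = 1.0: 0.25/1.25 = 0.20
- d1 = 0.8, d2 = 0.3: 0.06/√(1.16 × 1.0225) = 0.055
- either effect zero: r = 0

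**Step 2: spurious slope in Model A**

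Adjusting for the baseline score leaves a within-arm predictor variance of 1 − 0.3² = 0.91 in direction 1 and 1 − 0.5² = 0.75 in direction 2. The expected slope is (d²/4) / (residual variance + d²/4). At d = 0.8:

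- Direction 1: 0.16/(0.91 + 0.16) = 0.150 (simulated 0.151 at N = 60)
- Direction 2: 0.16/(0.75 + 0.16) = 0.176 (simulated 0.180 at N = 60)

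The true within-arm slope is zero in both cases.

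**Step 3: rejection rate at nominal 5%**

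Simulation of Model A with 4,000 runs per setting and equal effects on both outcomes, shown as direction 1 / direction 2. Monte Carlo standard error near 5% is √(0.05 × 0.95/4000) = 0.3 percentage points.

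| Effect d | N = 40, no group | N = 60, no group | N = 100, no group |
|---|---|---|---|
| 0 | 5.1% / 4.7% | 5.2% / 4.6% | 5.0% / 5.3% |
| 0.3 | 5.8% / 5.6% | 6.0% / 5.8% | 5.2% / 5.4% |
| 0.5 | 6.2% / 6.8% | 7.6% / 8.7% | 9.5% / 10.2% |
| 0.8 | 13.8% / 16.3% | 18.4% / 22.0% | 30.0% / 35.0% |

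At d = 1.0, a separate simulation of direction 1 (6,000 runs) gives 34% at N = 60 and 53% at N = 100.

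**Step 4: the same regressions with group added**

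Across every setting in the table and both directions, the rejection rate is 4.4% to 5.9% and the mean slope is within ±0.005 of zero.

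**The case against.** The omission itself cannot be disputed, because the Table 3 footnotes close the covariate list. The arguments on the other side concern its consequences.

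- **The harm is conditional.** It needs a real effect on both outcomes. At 0.3 SD the error rate is near nominal, and at 0.5 SD the induced correlation of 0.06 is under 0.4% of variance. The high rates need about 0.8 SD or more on both, and nothing in the SAP suggests effects of that size. The tabulated cases also take the two effects as equal; one strong and one weak effect gives little bias (0.055 for 0.8 with 0.3). All of this stands and limits the size of the concern.
- **Mediation.** If gait analysis improves family-centred services and these in turn improve motor function, the between-arm part of the association is signal. That is possible, but the pooled model cannot tell it from two parallel effects. The within-arm slope still estimates the relation of interest, so mediation is no reason to leave arm out.
- **The wording is cautious.** Hypothesis c) speaks only of association, and the synopsis says what it could indicate. A pooled association is a legitimate descriptive quantity. The synopsis nevertheless gives it a practical use that a purely treatment-induced association would not support.
- **Table 2 gives a warning.** It reports the group effects on both outcomes, so a reader can see whether the precondition is met. That flags the problem without correcting the Table 3 estimates.

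**Conclusion.** The concern holds. As specified, Table 3 cannot separate a relation between parents' experience of care and motor improvement from a treatment effect on both, and the problem grows as the primary hypothesis and hypothesis b) both succeed. The distortion is negligible if either effect is absent or small, modest at 0.5 SD on both (7.6–8.7% false positives at N = 60) and serious at 0.8 SD (18.4–22.0% at N = 60, 30–35% at N = 100).

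These figures rest on an assumed N, 1:1 arms, equal effects and assumed baseline correlations. The direction of the bias and its removal by the group term do not depend on the particular values. Model A was simulated; Model B shares the flaw because its added covariates do not carry the arm. The primary between-group comparison is unaffected. This should be changed, but it does not threaten the main result.

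**What to change.** Add randomised group as a covariate to Models A and B in both parts of Table 3, and amend the Data analyses text and the Table 3 footnotes to match, so that the association is estimated within arms. A group-by-predictor interaction or within-arm slopes could be reported as exploratory. The pooled model without group could be kept as a sensitivity analysis.

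The cost is one degree of freedom per model and a footnote change. The variable is already in the data set. If the arms do differ on the predictor, some precision is lost because between-arm variation no longer feeds the slope, but that is the variation that cannot be interpreted safely.

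### Hypothesis c) raises the direction of the FCS–motor relation, but the two Table 3 regressions swap the same two variables with mismatched baselines and cannot show direction

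*SAP*

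**What the plan says.** Under Secondary hypotheses and outcome, item c) reads "The experience of FCS is associated with gross motor function improvement in a unidirectional or bidirectional relation", to be reported as multiple regression in Table 3. The Aim is more modest: "investigate potential associations between perceived experience of FCS and gross motor function improvement".

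Data analyses defines two regressions.

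- **Regression 1.** "MPOC-20 52-weeks follow-up domain scores will be used as the dependent variable", with GMFM-66 change from 0 to 52 weeks entering as "score as the independent variable, adjusted for baseline GMFM-66 score (table 3, model A").
- **Regression 2.** GMFM-66 change is the outcome, with "MPOC-20 52-weeks follow-up domain scores as the independent variable, adjusted for baseline MPOC-20 domain scores".

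The Table 3 footnotes agree with the text; for regression 2 they give "Model A: Adjusted for baseline MPOC-20 domain scores". Model B adds sex, age, BMI SDS, CP type and GMFCS level to both regressions and restores neither missing baseline. In Table 2, where GMFM-66 change is also a dependent variable, the footnote is "Model B: Model A adjusted for relevant baseline score".

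No rule says how the two halves of Table 3 are to be combined into a statement about direction.

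**The concern.** The only reason the SAP offers for fitting both regressions is the wording of c), which raises a one-way or two-way relation. A reader who finds one half of Table 3 significant and the other not will be inclined to read that as direction. The design cannot support this. GMFM-66 is measured only at baseline and 52 weeks, so its change ends when the 52-week MPOC-20 is taken and there is no time order to use. Swapping outcome and predictor adds no information.

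The two halves do differ in which baseline they adjust for. Each leaves out the baseline of its own outcome, so each can pick up an association that runs only through that baseline.

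The Study synopsis gives the result practical weight. It would use an association to find families who might gain from enhanced information and care, with the aim of improving the child's motor function. That already reads the relation from services to motor change.

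**Working it through.** **Inputs.** From the SAP: the two model definitions above, and alpha 0.05 (sidedness not stated; two-sided assumed). The SAP gives no n, SD or correlation and states no figure for c), so there is nothing of its own to reproduce. All values below are assumptions.

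**Step 1: matched covariates give one test.** With the same k covariates and one domain per model, the t for Y on X and for X on Y is t = r·√[df/(1−r²)], where r is the partial correlation and df = n − k − 2. The formula is symmetric in X and Y. In one simulated data set (n=60, both baselines, df = 60 − 2 − 2 = 56), t = 3.681 and p = 0.000524 in both directions, with r = 3.681/√(3.681² + 56) = 0.44. The SAP's own covariate sets on the same data gave t = 3.966 and 3.744. That gap comes only from the unequal adjustment. The identity needs no assumption about n or effect size.

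**Step 2: one-way effects.** Write m0, m1 for MPOC-20 at baseline and 52 weeks, g0 for baseline GMFM-66 and d for its change. Baselines are independent with variance 1; the 0–52 week correlations are 0.6 and 0.8, giving residual SDs √(1−0.36) = 0.8 and √(1−0.64) = 0.6.

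*m1 acts on GMFM-66 (0.2):* d = −0.2·g0 + 0.2·m1 + 0.6·e.
- Regression 1 (given g0): r = 0.2/√(1 × 0.40) = 0.316
- Regression 2 (given m0): r = 0.128/√(0.64 × 0.4256) = 0.245
- Both baselines: r = 0.128/√(0.64 × 0.3856) = 0.258

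The regression 1 coefficient is 0.2/0.40 = 0.50 without m0 and 0.128/0.3856 = 0.33 with it.

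*d acts on m1 (0.4):* m1 = 0.6·m0 + 0.4·d + 0.8·u.
- Regression 1: r = 0.144/√(0.36 × 1.0576) = 0.233
- Regression 2: r = 0.16/√(0.40 × 0.704) = 0.302
- Both baselines: r = 0.144/√(0.36 × 0.6976) = 0.287

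Simulated rejection rates (n=60, Model A, 10,000 trials each):

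| Truth | Regr. 1 | Regr. 2 | Both baselines | Regr. 1 and 2 disagree |
|---|---|---|---|---|
| m1 acts on GMFM-66 | 69% | 47% | 50% | 29% |
| d acts on m1 | 43% | 65% | 60% | 30% |

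In each row the regression whose outcome is truly driven is the less often significant, so a discordant pair tends to point the wrong way. Over n = 40 to 80 and correlations from 0.5/0.9 to 0.7/0.7, disagreement is 7–38%. With both baselines entered it is 0.

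A separate simulation with larger assumed effects (3,000 runs, n=60) included a shared cause with no effect either way. Exactly one half was significant in 11% of runs, nearly always regression 2. Motor change driving FCS gave much the same pattern, with only regression 2 significant in 13%. The two truths cannot be told apart from Table 3.

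**Step 3: effects that run only through a baseline.** If only m0 acts on GMFM-66 with effect b, then d = −0.2·g0 + b·m0 + 0.6·e, and b explains b²/(0.40 + b²) of the change variance: 2%, 9%, 18% and 29% for b = 0.1 to 0.4. Given both baselines, the association between m1 and d is zero.

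| b | 0.1 | 0.2 | 0.3 | 0.4 |
|---|---|---|---|---|
| Regr. 1, Model A | 12% | 31% | 54% | 74% |
| Regr. 1, Model B | 11% | 29% | 51% | 71% |

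Regression 2 stays at about 5%. Over the same range of n and correlations, Model A gives 8–16%, 21–46% and 38–72% at b = 0.1, 0.2 and 0.3.

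If only g0 acts on m1 (0.1 to 0.5), regression 2 rejects in 6/9/14/19/25%, mostly with a negative sign because g0 is negatively related to its own change. In Model B this is 5/6/8/10/12%; there GMFCS level, taken as a median split of a variable correlated 0.8 with g0, partly replaces the missing baseline. With both baselines entered, both situations return to about 5%.

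**Step 4: no cross-effect at all.** Both SAP regressions reject in about 5%, so type I error is not inflated in that case.

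**The case against.** The best defence is that the SAP never claims to infer direction. Item c) commits to neither option, the Aim and the Table 3 title speak of associations, and the a priori interpretation rules cover only the between-group MPOC-20 comparison. This is true: there is no decision rule to fault, and the disagreement rates matter only if someone reads direction into them. But item c) names direction as something to be found, and the swapped models have no other stated purpose.

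Second, where baseline MPOC-20 truly affects motor change, 52-week MPOC-20 and motor change are correlated, so regression 1 detects something real. Conditioning on baseline MPOC-20 also removes stable differences between families, which the synopsis may want to keep. Both points are fair, and the association in step 3 is absent only given both baselines. However, the SAP conditions on baseline MPOC-20 in one half of Table 3 and not in the other, so it has not chosen either question consistently.

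Third, Table 2 is a randomised comparison and Table 3 an observational association, so different covariates are not in themselves a contradiction. That stands. The contrast shows only that baseline GMFM-66 is thought relevant to GMFM-66 change in one table and dropped without explanation in the other.

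Finally, c) is a secondary hypothesis and every size above rests on assumed inputs. This limits the weight of the point but not the algebra.

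**Conclusion.** The point holds. Table 3 cannot show direction: with matched covariates its two halves are one test, and as written they differ only through unequal baseline adjustment. The identity in step 1 is exact for one domain per model.

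The sizes depend on the assumed n, correlations and mechanism. For moderate one-way effects the halves disagree in about 29–30% of trials at n=60, and in 7–38% over the range examined. An effect of baseline MPOC-20 alone brings regression 1 to 12–74%; an effect of baseline GMFM-66 alone brings regression 2 to 25% at most in Model A. These simulations assume no measurement error and independent baselines.

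The consequence is confined to hypothesis c) and its use in the synopsis. The primary analysis and hypotheses a) and b) do not depend on it. The SAP should be corrected on this point.

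**What to change.** 1. In Data analyses and the Table 3 footnotes, enter both baseline GMFM-66 and the same-domain baseline MPOC-20 in every Table 3 model, A and B, with one domain per model.
2. Report one partial association per domain. The second half of Table 3 then carries no further test and can be dropped, or kept only to show the coefficient on the other scale.
3. Delete the phrase in c) about a one-way or two-way relation. The Aim, which asks only for associations, is still met.
4. If time order is of interest, add a model such as 26-week MPOC-20 predicting 52-week GMFM-66, adjusted for both baselines. Label it exploratory and state that it answers a different question from the contemporaneous association.

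The cost is a wording change and one already collected covariate per model, hence one degree of freedom. The directional claim is lost, and the estimate becomes an association given where family and child started; the text should say so.

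### The Table 2 comparison of ΔGMFM-66 is valid but adjusts only for its baseline score, leaving age and GMFCS level unused as an option for precision and chance imbalance

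*SAP*

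**What the plan says.** Hypothesis b (SAP, Secondary hypotheses and outcome) compares the change in GMFM-66 from baseline to 52 weeks between the randomised groups, with the result in Table 2. The Table 2 footnotes fix the models:

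- "Dependent variable: ΔGMFM-66 or ΔMPOC-20 domains", with randomisation group as the independent variable.
- "Model A: Unadjusted model".
- "Model B: Model A adjusted for relevant baseline score".

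The Data analyses section gives the same rule: a linear model "in which relevant baseline scores are entered as covariates (table 2, model B"). No other covariate is named for the group comparison. The sentence that follows lets the model specification depend on distributional properties, but it does not open the covariate list.

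Age and GMFCS level are among the variables listed under Descriptive outcome ("At inclusion the following descriptive outcomes were collected") and will be shown by group in Table 1. They enter a model only in Table 3. In its second panel the ΔGMFM-66 "score will be used as the dependent variable and MPOC-20 52-weeks follow-up domain scores as the independent variable, adjusted for baseline MPOC-20 domain scores"; for that panel, "potential confounding variables as sex, age, BMI SDS, CP type and GMFCS level will be adjusted for as covariates (table 3, model B").

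**The concern.** In a randomised comparison, a covariate fixed before allocation and related to the outcome removes residual variance and corrects for whatever chance imbalance it has between the arms. Age and GMFCS level are candidates for ΔGMFM-66. Listing them as potential confounders in a regression of that outcome presumes that some relation to it is plausible, since a variable unrelated to the outcome cannot confound.

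If they do carry information beyond baseline GMFM-66, the planned Model B gives a wider interval and less power for hypothesis b than the data allow. If Table 1 then shows the arms differing in age or GMFCS level, the plan has no pre-specified way to account for it in this comparison, and any later adjustment would be post hoc. By the SAP's Introduction, the 52-week examinations ended in July 2017, so the number of children is fixed and the analysis model is one of the few remaining ways to gain precision.

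**Working it through.** **No figure to reproduce.** The SAP gives no sample size, standard deviation or explained variance for ΔGMFM-66. What follows is an illustration over assumed ranges.

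**Inputs**
- From the SAP: alpha 0.05 and 95% confidence intervals (two-sided assumed); present Model B = group + baseline score.
- Assumed: n = 40, 60 or 80 children in total, allocated 1:1.
- Assumed: R² = 0 to 0.30, the share of the variance left after group and baseline GMFM-66 that age and GMFCS level explain.

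**Precision.** With k baseline covariates that vary at random between the arms, the expected variance of the group coefficient is proportional to (residual variance) × (n − 3)/(n − 3 − k). Going from k = 1 (baseline score) to k = 3 (plus age and GMFCS level):

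SE ratio = √[(1 − R²) × (n − 4)/(n − 6)]

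The CI-width ratio multiplies this by the ratio of the 97.5% t quantiles on n − 5 and n − 3 degrees of freedom. Example, n = 60 and R² = 0.10: √(0.90 × 56/54) = 0.966; with the t quantiles, 0.967.

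| R² | CI ratio, n = 40 | n = 60 | n = 80 | Change in width |
|---|---|---|---|---|
| 0 | 1.031 | 1.019 | 1.014 | 1–3% wider |
| 0.05 | 1.005 | 0.993 | 0.988 | within about 1% |
| 0.10 | 0.978 | 0.967 | 0.962 | 2–4% narrower |
| 0.20 | 0.922 | 0.912 | 0.907 | 8–9% narrower |
| 0.30 | 0.863 | 0.853 | 0.848 | 14–15% narrower |

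A simulation of the two models (4,000 replicates per cell) agreed with these ratios to within 0.003. Interval coverage stayed near 95% under both models, so the present model is valid.

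**Break-even.** Setting the SE ratio to 1 gives R² = 2/(n − 4): 2/36 = 0.056 at n = 40, 2/56 = 0.036 at n = 60 and 2/76 = 0.026 at n = 80.

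**Power.** For a comparison with nominal 80% power under the present Model B, the normal approximation gives Φ[(1.960 + 0.842)/(SE ratio) − 1.960]. At n = 60 this is 78.6% for R² = 0, 82.6% for 0.10, 86.8% for 0.20 and 90.8% for 0.30.

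**Chance imbalance.** Assume simple 1:1 randomisation and half the children at GMFCS level II. The SD of the between-arm difference in that proportion at n = 60 is √(4 × 0.25/60) = 0.129, or 13 percentage points. For age, 95% of chance differences in means lie within ±1.96 × √(4/n) SD: ±0.62 SD at n = 40, ±0.51 at n = 60 and ±0.44 at n = 80. Stratified allocation would reduce these figures for any factor it used.

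**The case against.** A reader might infer that the SAP contradicts itself by treating age and GMFCS level as predictors of motor change in Table 3 and ignoring them in Table 2. The documents do not support this. The SAP calls them potential confounders, and the same list ("Model B: Model A adjusted for sex, age, BMI SDS, CP type and GMFCS level") is used in the panel where MPOC-20 is the dependent variable, so it is a general confounder set. MPOC-20 scores are not randomised and need confounder control; randomisation group does not. Different covariate sets for these two purposes are normal.

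Table 3 also says nothing about added value. Its ΔGMFM-66 panel adjusts for baseline MPOC-20 and not for baseline GMFM-66, whereas Table 2 Model B already contains baseline GMFM-66. Only the variance explained beyond that score counts, and with children limited to ages 5 to 8 and GMFCS levels I and II it may be small.

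A further tempting inference is that precision is certainly lost, or that imbalance biases the result. Neither follows. Below break-even the extra covariates slightly widen the interval. The present estimate is unbiased over randomisation, baseline GMFM-66 already absorbs part of any imbalance in motor level, and whether allocation was stratified cannot be seen in the SAP.

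All of this stands. It removes any claim of error, and it makes the benefit conditional. It does not remove the asymmetry between a small, bounded cost and a possibly useful gain. The choice of age and GMFCS level from the five listed variables is a judgement about which are most likely to relate to motor change; the SAP does not rank them.

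**Conclusion.** The planned comparison of ΔGMFM-66 is valid, and there is no inconsistency between Tables 2 and 3. What holds is narrower: two baseline variables already in hand are not used in the randomised comparison for hypothesis b, although they could sharpen the estimate and cover chance imbalance beyond baseline GMFM-66.

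For an assumed 40 to 80 children, the possible effect runs from an interval 1–3% wider, if the covariates explain nothing, to one 14–15% narrower, if they explain 30% of the remaining variance. Nothing in the SAP says where in that range the trial lies. The matter touches one row of Table 2 and a secondary hypothesis; the superiority rule under Data interpretation uses only the MPOC-20 domains and is unaffected. It is a cheap improvement worth making, not the correction of a fault.

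**What to change.** For the ΔGMFM-66 row of Table 2, define Model B as randomisation group + baseline GMFM-66 + age (continuous) + GMFCS level (I/II). State that this model gives the estimate for hypothesis b; the SAP now reports Models A and B without saying which one answers it. Keep Model A as the unadjusted companion. The MPOC-20 rows can stay as they are.

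This takes one sentence in Data analyses and one in the Table 2 footnote, fixed before outcomes are compared by group. If that comparison has already been made, report the added model as a labelled sensitivity analysis. No new data are needed. The price is two residual degrees of freedom, at most about 3% in interval width at n = 40.
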